#### 5.4.2 Dose de-escalation rules

If at any time, safety stopping rules are met as outlined in section 13.4, enrollment will be paused and one of two contingency dosing strategies for subsequent patients will be considered based upon the nature of the observed dose-limiting toxicities. The choice of contingency dose strategy will be made by the study committee in consultation with Pfizer and ImmunityBio.

Upon initial activation of this study, two of the first three enrolled patients in Cohort A experienced cycle 1 DLTs. This met stopping criteria for our interim monitoring rule and Contingency A was enacted on 1/8/2020. Should the new stopping rule as outlined in section 13.4 be met, Contingency B or C as outlined below will be considered for Cohort A. Cohort B has not yet met any stopping critiera.

- Contingency A: Palbociclib 100 mg daily on days 1-21 and ganitumab 18 mg/kg on days 1 and 15
- Contingency B: Palbociclib 75 mg daily on days 1-21 and ganitumab 18 mg/kg on days 1 and 15

- Contingency C: Palbociclib 75 mg daily on days 1-21 and ganitumab 12 mg/kg on days 1 and 15

If a contingency dosing strategy is implemented, the same monitoring rule will apply (starting anew with next enrollment). If criteria are met again for the toxicity monitoring rule, the protocol will be flagged for amendment. Any toxic death will be cause for review by the DSMB and the study committee for consideration of protocol amendment.

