#### Definition of Dose-Limiting Toxicity

DLT is defined as any of the following events that are possibly, probably or definitely attributable to palbociclib or ganitumab. A DLT may occur in any cycle and will guide dose modifications, but only DLTs occurring in the first cycle will be used for implementation of the safety monitoring rule (Section 13.4).

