#### *Non-Hematological DLT:*

- Any Grade 3 or higher non-hematological toxicity attributable to palbociclib or ganitumab with the specific exclusion of:
  - Grade 3 nausea and vomiting, anorexia, diarrhea or dehydration resolving to  $\leq$  grade 2 within 72 hours (note that grade 3 diarrhea requiring hospitalization would constitute DLT).
  - Grade 3 AST or ALT liver enzyme elevation that return to  $<$  grade 2 within 7 days (except as below if bilirubin also elevated). If grade 3 liver enzyme elevation occurs, palbociclib and ganitumab should be held and liver enzymes rechecked within 4 days of initial date of grade 3 abnormality to determine if DLT criteria have been met. See also Section 6.4.

**Recall:** For the purposes of this study the ULN for ALT is defined as 45 U/L and for AST is 30 U/L.

- Grade 3 hypophosphatemia, hypokalemia, hypocalcemia or hypomagnesemia responsive to oral supplementation within 72 hours.
- Grade 2 elevation of AST and/or ALT WITH total bilirubin  $> 2 \times$  ULN, in the absence of cholestasis.
- Any Grade 2 non-hematological toxicity that persists for  $\geq 7$  days and is considered sufficiently medically significant or sufficiently intolerable by patients that it requires treatment interruption.
- Any non-hematologic toxicity that results in delay in start of subsequent cycle by  $> 14$  days.

*Hematological DLT:*

- Hematological dose limiting toxicity is defined as:
  - Grade 4 thrombocytopenia or grade 4 neutropenia of any duration, in the absence of bone marrow disease; or
  - Grade 3 or higher febrile neutropenia with or without documentation of infection; or
  - Grade 3 thrombocytopenia in association with a grade 2 or higher bleeding episode; or
  - Delay in the start of subsequent cycle by  $> 14$  days due to thrombocytopenia or neutropenia, in patients without known bone marrow disease.

Patients with bone marrow metastatic disease at study entry will not be evaluable for hematologic DLT for the purposes of evaluating the toxicity monitoring rule. Such patients will follow the dose modification criteria in Section 6.2.1 in the setting of defined hematologic DLT.

Any Grade 5 toxicity that is possibly, probably, or definitely attributable to palbociclib or ganitumab will be considered a DLT.

Management and dose modifications associated with the above adverse events are outlined in Section 6.

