### 13.2 Sample Size, Accrual Rate and Study Duration

A total of 15 response evaluable patients with Ewing sarcoma (Cohort A) and 12 response evaluable patients with SDH-deficient GIST (Cohort B) will be required to address the primary objective. Patients who are not eligible and/or evaluable for response will be replaced.

Therefore, given potentially inevaluable patients a maximum of 33 patients with Ewing sarcoma or SDH-deficient GIST are expected to enroll.

Study Duration: We anticipate that 1-2 patients with Ewing sarcoma and 1-2 patient per GIST per month will be available for enrollment. Enrollment of the maximum sample size of 33 patients with Ewing sarcoma and GIST will require approximately 18-24 months.

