#### **13.4.1 Cohort A toxicity monitoring plan**

For Cohort A, the original two-stage toxicity monitoring rule was triggered with 2 DLTs out of the first 3 evaluable patients. A new one-stage design has been developed for the remaining 12 patients, all of whom will be treated at a lower dose level than the first 3 patients (contingency A, see Section 5.4.2).

Enroll up to 12 toxicity evaluable patients. If at any time 3 or more patients have a first cycle DLT, enrollment will be paused, the trial will be reviewed by the study committee and the DSMC, and a lower dose level will be considered as outlined in Section 5.4.2. If fewer than 3 of 12 patients have a first cycle DLT, the dose level will be considered sufficiently safe for further study. This rule has the following operating characteristics. The null hypothesis is that the proportion of patients with a Cycle 1 DLT is  $\geq 39\%$  versus the alternative that the proportion with a Cycle 1 DLT is  $\leq 9\%$ . The power is 91.3% and the type 1 error is 9.5%.

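### A toxic death triggers a review under 5.4.2 but no enrolment hold while that review is pending; the only mandatory safety pause is at three Cycle 1 DLTs in a cohort.

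*Combined protocol and SAP*

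**What the plan says.** Section 5.4.2 attaches the pause to the DLT-count rule: "If at any time, safety stopping rules are met as outlined in section 13.4, enrollment will be paused". It treats deaths in a separate sentence at its end: "Any toxic death will be cause for review by the DSMB and the study committee for consideration of protocol amendment". That sentence contains no hold and no time limit for the review.

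The count rule is the same in both cohorts (13.4.1 and 13.4.2), with up to 12 toxicity-evaluable patients in each: "If at any time 3 or more patients have a first cycle DLT, enrollment will be paused". Review by the study committee and the DSMC then follows, and a lower dose is considered.

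Section 5.4.1 settles how a death enters that count. On the one hand, "Any Grade 5 toxicity that is possibly, probably, or definitely attributable to palbociclib or ganitumab will be considered a DLT". On the other, "only DLTs occurring in the first cycle will be used for implementation of the safety monitoring rule". Among the haematological events that also count as one DLT is "Grade 4 thrombocytopenia or grade 4 neutropenia of any duration, in the absence of bone marrow disease".

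For accrual, Section 13.2 says: "We anticipate that 1-2 patients with Ewing sarcoma and 1-2 patient per GIST per month will be available for enrollment". It also says: "Enrollment of the maximum sample size of 33 patients with Ewing sarcoma and GIST will require approximately 18-24 months".

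**The concern.** For three Cycle 1 DLTs the plan prescribes both steps, pause and review. For a drug-related death it prescribes only the review. Three patients with brief Grade 4 neutropenia in Cycle 1 therefore force a pause. One or two drug-related deaths in Cycle 1 without a third Cycle 1 DLT do not, and nor does any number of deaths after Cycle 1, although treatment may last 12 cycles.

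The combination had not been studied before (1.1). At stake are the patients who could start the same regimen between an attributable death and the outcome of its review.

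**Working it through.** **1. The plan's own figures.** With 12 patients and a pause at 3 or more DLTs (13.4.1, 13.4.2):
- Power: P(Bin(12, 0.09) ≤ 2) = 0.913, against the stated 91.3%.
- Type 1 error: P(Bin(12, 0.39) ≤ 2) = 0.095, against the stated 9.5%.

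Both reproduce. The count rule is correctly calibrated for what it measures.

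**2. Search for another hold.** Sections 5.4, 5.6, 7, 12.2 and 13 contain no other mandatory safety pause. The stop at 0 responders of 7 in Cohort B (13.3.2) is a futility rule.

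**3. How often the count rule would supply the pause anyway.** Given one Cycle 1 death, the rule is missed if at most one of the other 11 patients has a Cycle 1 DLT, P(Bin(11, p) ≤ 1):

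| DLT rate p | Source | Rule not reached |
|---|---|---|
| 9% | plan's acceptable rate | 74% |
| 20% | assumed | 32% |
| 39% | plan's unacceptable rate | 3.5% |

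These figures show how often the count rule backs up the review. They do not measure exposure. A death after Cycle 1 adds nothing to the count at any p.

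**4. Exposure if a death occurs during accrual.** Expected new starts m = monthly rate × review weeks × 7/30.44. The protocol sets no review time, so 2-4 weeks is assumed. The stated accrual rate is 1-2 per month per cohort. The stated 18-24 months for 33 patients implies less: 33/24 to 33/18 = 1.375 to 1.833 per month in total, or 0.69 to 0.92 per cohort if split evenly (assumed).

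| Rate per month | 2 weeks | 4 weeks |
|---|---|---|
| 0.69 | 0.32 | 0.63 |
| 0.92 | 0.42 | 0.84 |
| 1 | 0.46 | 0.92 |
| 2 | 0.92 | 1.84 |

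With random arrivals (assumed), P(at least one start) = 1 − exp(−m), from 0.27 at m = 0.32 to 0.84 at m = 1.84.

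**5. Exposure without conditioning on a death.** The documents give no toxic-death rate. For an assumed per-patient rate f, expected starts per 12-patient cohort are at most 12 × f × m:
- f = 1%: 12 × 0.01 × (0.32 to 1.84) = 0.04 to 0.22
- f = 2%: 12 × 0.02 × (0.32 to 1.84) = 0.08 to 0.44

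These are upper bounds, because a death late in accrual, or after it, leaves few or no starts to prevent.

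**6. Which cohort.** Cohort A moved to 100 mg on 1/8/2020 (5.4.2); the Cohort B amendment was developed in December 2020 (13), about 11 months later. At 0.69 per month, 11 × 0.69 = 7.6 of the 12 Cohort A patients would have started by then; at 1 per month, 11. Actual accrual is not stated. In a cohort opening from zero with even spacing, 10-11 of 12 are still to start when the first patient reaches Cycle 2, and 5-6 when the sixth does. That picture fits Cohort B.

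**7. Extra pauses from a death trigger.** Let t be the Cycle 1 DLT rate, including deaths, and f the Cycle 1 fatal rate (assumed). No pause occurs only with no death and at most two DLTs, so P(pause) = 1 − Σ(k = 0 to 2) C(12,k)(t − f)^k(1 − t)^(12−k).

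| t | No death trigger | f = 0.5% | f = 1% | f = 2% |
|---|---|---|---|---|
| 9% | 8.7% | 13.0% | 17.3% | 25.4% |
| 39% | 90.5% | 90.7% | 91.0% | 91.4% |

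Adding an independent later-cycle fatal rate g gives 1 − (1 − P)(1 − g)^12. At t = 9% this is 27% for f = g = 1% and 41% for f = g = 2%. Both are upper bounds, because a death after accrual closes holds nobody up.

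**The case against.** The best counter-argument is that the plan already treats deaths more strictly than DLTs: one toxic death, in any cycle, obliges two bodies to review, whereas the count rule waits for three events. The two rules also do different jobs. Section 13.4 is a calibrated tolerability rule, and the death sentence stands apart from it. Setting three neutropenias against two deaths therefore overstates the contrast. This stands. A reader might infer that deaths after Cycle 1 go unexamined, or that enrolment must continue after a death. The documents support neither: 5.4.2 requires the review in any cycle, and nothing stops the reviewers from holding enrolment.

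Information also travels fast. Serious events reach the Overall Principal Investigator within 24 hours (7.6.1), fatal ones go to the palbociclib supplier at once (7.9), unexpected fatal drug-associated events go to the FDA within 7 days (7.7), and the DSMC can meet more often than quarterly (12.2). Slots are reserved through the Study Coordinator (3), so a discretionary hold is workable today. These provisions shorten the interval. None stops enrolment.

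The exposure is also conditional on what should be a rare event, and the extra pauses would fall mainly where the regimen is acceptable (step 7). At least possible attribution is a low threshold in relapsed disease with performance status down to 50%. Both points stand and limit the size of the finding. Each added pause would nevertheless follow a death at least possibly due to study drug, and would end once the reviewers agree to resume.

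**Conclusion.** The concern holds in a limited form: after a toxic death, the plan mandates a review but leaves the enrolment hold during it to discretion. The reading of the text needs no assumption. The size does: a 2-4 week review, the accrual rates in 13.2 with an even split for the slower ones, and a fatal rate that the documents do not give. On these, the gap is worth 0.3-1.8 starts per death during accrual, but no more than about 0.04-0.22 starts per cohort at a 1% fatal rate. The remaining exposure is probably larger in Cohort B.

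A reader might also infer that the 3-of-12 rule is faulty. It is not: its stated power and type 1 error reproduce, and they describe the DLT count alone. The change is worth making because it is cheap and concerns patient safety, not because the expected number of patients is large.

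**What to change.** In 5.4.2 only, add:

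> Any Grade 5 event at least possibly attributable to palbociclib or ganitumab, in any cycle or within 30 days of the last dose, pauses new enrollment to that cohort until the study committee and the DSMC have reviewed it and agreed to resume. This pause is separate from the Section 13.4 rule: it does not by itself trigger contingency dosing or restart the DLT count, and a Cycle 1 death still counts as one DLT.

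In the same section, change DSMB to DSMC, the body named in 12.2 and 13.4. Leave 13.4.1 and 13.4.2 untouched. Placing the pause there could make a single death read as meeting the rule that leads to contingency dosing, and would set it beside operating characteristics that do not include it.

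The cost is a short amendment using existing committees, reporting lines and slot reservation. Sample size, endpoints and analysis do not change. The downside is a short accrual hold per event (about 0.3-1.8 enrolments delayed), including for deaths judged only possibly related, and more frequent pauses in an acceptable regimen.

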## 5.5 General Concomitant Medication and Supportive Care Guidelines

### 5.5.1 Concomitant Medications

- 5.5.1.1 No other cancer chemotherapy or anticancer therapies are allowed except local measures specified in section 5.3.3.
- 5.5.1.2 Appropriate antibiotics, blood products, anti-emetics, fluids, electrolytes and general supportive care are to be used as necessary (see Section 5.5.2).
- 5.5.1.3 Patients may not receive corticosteroids EXCEPT under the following conditions:
  - Physiologic replacement for patients with adrenal insufficiency
  - As needed to manage allergic reactions
  - To prevent transfusion reactions
  - Inhaled or topical administration
  - In patients with metastatic CNS disease, use of doses that have been stable or tapering since enrollment.
- 5.5.1.4 Subjects must not receive any of the QT prolonging agents in Appendix B, Table 12. QT prolonging agents in Appendix B, Table 13 are to be used with caution.
- 5.5.1.5 Subjects must not receive strong CYP3A inducers or inhibitors (delineated in Appendix B, Table 10) within 7 days of enrollment and while on protocol therapy. Subjects receiving moderate CYP3A inhibitors should be monitored (see Appendix B, Table 11).

Subjects receiving concomitant medications metabolized by CYP3A enzymes should be monitored at the discretion of the investigator, particularly if the concomitant medication has a narrow therapeutic window and/or is known to rely strongly on one of these isoenzymes for its metabolism. Such medications may have an interaction with palbociclib.

Patients must avoid consumption of grapefruit products, and Seville oranges or products containing the juice of each while on protocol therapy, due to potential CYP3A4 interaction with the study medications. Orange juice is allowed.

Please refer to the palbociclib and ganitumab Investigator's Brochures for additional drug interaction information.

## 5.5.2 Supportive Care Guidelines

### 5.5.2.1 Use of Myeloid Growth Factors

Myeloid growth factors are only to be utilized in the setting of grade 3 or 4 neutropenia together with documented invasive fungal infection, bacteremia, or fever with sepsis physiology. The overall Principal Investigator should be notified in the event of myeloid growth factor use. Patients who receive myeloid growth factor for grade 3 neutropenia will be excluded from assessment of dose-limiting neutropenia in that cycle. If a patient receives myeloid growth factor, palbociclib and ganitumab must not be resumed until at least 48 hours following the last administered dose of short acting myeloid growth factor and until at least 7 days following the last administered dose of long-acting myeloid growth factor.

### 5.5.2.2 Antiemetics

Palbociclib may be emetogenic, but routine use of prophylactic antiemetics is not indicated. For patients who develop nausea, appropriate non-corticosteroid antiemetics should be utilized according to institutional guidelines (aprepitant is discouraged; see Appendix B).

## 5.6 Criteria for Taking a Participant Off Protocol Therapy

Duration of therapy will depend on individual response, evidence of disease progression, and tolerance. Treatment may continue for up to 12 cycles or until one of the following criteria applies:

- Disease progression
- Intercurrent illness that prevents further administration of treatment
- Dose-limiting or other toxicity that meets criteria for removal from protocol therapy (see Section 6)
- Participant demonstrates an inability or unwillingness to comply with the oral medication regimen and/or documentation requirements
- Participant decides to withdraw from the protocol therapy
- Pregnancy
- General or specific changes in the participant's condition render the participant unacceptable for further treatment in the judgment of the treating investigator

Participants will be removed from the protocol therapy when any of these criteria apply. The reason for removal from protocol therapy, and the date the participant was removed, must be

documented in the case report form (CRF). Alternative care options will be discussed with the participant.

When a participant is removed from protocol therapy and/or is off of the study, the participant's status must be updated in OnCore in accordance with [REGIST-OP-1](#).

In the event of unusual or life-threatening complications, treating investigators must immediately notify the Overall PI, [REDACTED] [REDACTED]

### 5.7 Duration of Follow Up

Participants will return to the study center for adverse event follow-up approximately 30 days from last dose of protocol therapy. This period may be extended until resolution of any ongoing adverse events. Participants removed from protocol therapy for unacceptable adverse event(s) will be followed until resolution or stabilization of the adverse event. For participants unable to return to the study center for the planned 30-day follow-up visit, documentation of a clinic evaluation at their referring center is acceptable.

Patients will be followed for survival until 1 year from when the last dose of protocol therapy is given to the last enrolled participant. Return to the study center will not be required as part of survival follow-up.

### 5.8 Criteria for Taking a Participant Off Study

Participants will be removed from study when any of the following criteria apply:

- Completion of follow-up per section 5.7;
- Found to be ineligible, including participants who have repeat organ function laboratory studies obtained within 5 days of Cycle 1, Day 1 that do not meet entry eligibility requirements. Participants who are found to have a diagnosis other than Ewing sarcoma/PNET, or SDH-deficient GIST during the course of study therapy may continue on protocol therapy only if evidence of clinical benefit and only after discussion with the overall Principal Investigator. Such patients will be replaced for the purposes of evaluating the primary aim of the study.;
- Lost to follow-up;
- Withdrawal of consent for data submission;
- Death.

The reason for taking a participant off study, and the date the participant was removed, must be documented in the case report form (CRF).

## 6 DOSING DELAYS/DOSE MODIFICATIONS

Dose delays and modifications will be made as indicated in the following text and table(s). The descriptions and grading scales found in the revised NCI Common Terminology Criteria for

Adverse Events (CTCAE) version 5.0 will be utilized for guiding dose delays and dose modifications.

### 6.1 Dose Modification for Dose-Limiting Toxicity

Patients with protocol-defined DLT (Section 5.4.1) will have palbociclib and ganitumab held. Except where noted below for specific target toxicities, palbociclib and ganitumab will be held until resolution of toxicity to  $\leq$  Grade 1 (or baseline, whichever is higher grade), and then palbociclib and ganitumab will be resumed with dose reduction according to Sections 6.2 (palbociclib) and 6.3 (ganitumab). If a patient cannot resume therapy within 21 days of holding palbociclib and ganitumab, they will be removed from protocol therapy.

Patients with recurrent DLT (regardless of category of DLT) despite this dose reduction are eligible for up to one additional dose reduction of palbociclib. Patients with recurrent DLT despite two dose reductions of palbociclib will be removed from protocol therapy. If a second dose reduction is required for toxicity related to ganitumab, the patient will be removed from protocol therapy.

Patients who meet criteria for permanent discontinuation of one study agent (e.g., severe allergic reaction), will be removed from protocol therapy altogether rather than continuing with monotherapy.

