### 5.2.2 Subsequent Cycles

Prior to the start of each subsequent cycle of therapy, patients without bone marrow involvement must meet all of the following criteria:

- No clinical or radiographic evidence of disease progression;
- Meet hematologic, renal, hepatic, and metabolic organ function requirements listed in Section 3.1.7, with the following exception:
  - ANC  $\geq 750/\mu\text{L}$
  - Platelets  $\geq 75,000/\mu\text{L}$  and transfusion independent, defined as not receiving a platelet transfusion for at least 5 days prior to CBC
- All other adverse events at baseline or  $\leq$  grade 2, whichever is lower.

Prior to the start of each subsequent cycle of therapy, patients who enrolled with bone marrow involvement as demonstrated on a clinically indicated bone marrow must meet all of the following criteria:

- No clinical or radiographic evidence of disease progression;
- Meet hematologic, renal, hepatic, and metabolic organ function requirements listed in Section 3.1.7, with the following exception:
  - ANC  $\geq 500/\mu\text{L}$
  - Platelets  $\geq 50,000/\mu\text{L}$  and transfusion independent, defined as not receiving a platelet transfusion for at least 5 days prior to CBC
- All other adverse events at baseline or  $\leq$  grade 2, whichever is lower.

Laboratory studies to meet these requirements may be obtained within 3 days of Day 1 of each cycle.

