## 5.4 Dose-Limiting Toxicity (DLT)

### 5.4.1 Definition of Dose-Limiting Toxicity

Toxicity will be graded using the CTCAE criteria, version 5. The CTCAE provides descriptive terminology and a grading scale for each adverse event listed. A copy of the CTCAE can be downloaded from the CTEP home page (<http://ctep.cancer.gov>). Any dose-limiting toxicity should be reported immediately via email to the overall Principal Investigator and to the Study Coordinator.

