## 6.4 Dose Modifications for Non-Hematologic Toxicity

### 6.4.1 Management of QTc Prolongation

QTc prolongation is a potential risk of palbociclib. In the setting of QTc prolongation, treat reversible causes such as serum electrolyte abnormalities and/or reduce usage of concomitant QTc-prolonging medications. See **Table 3** for recommended dose modifications in the setting of QTc prolongation.

**Table 3:** Palbociclib dose modifications for prolonged QTc

	Grade 2 QTc prolongation	Grade 3 QTc prolongation	Grade 4 QTc Prolongation
Reversible cause identified	Treat reversible causes  Initiate more frequent ECG monitoring according to investigator's best medical judgement until QTc < 480 msec  Continue at the same dose level	Treat reversible causes  Withhold treatment until QTc < 501 msec  Resume treatment at same dose  Initiate more frequent ECG monitoring according to investigator's best medical judgement until QTc < 480 msec	Remove from protocol therapy
No reversible cause identified	Initiate more frequent ECG monitoring according to investigator's best medical judgement until QTc < 480 msec  Continue at the same dose level	Withhold treatment until QTc < 501 msec  Resume treatment at one dose level below the current dose unless the patient has had two dose reductions of palbociclib in which case the patient must	Remove from protocol therapy

		
be removed from protocol therapy
 
Initiate more frequent ECG monitoring according to investigator's best medical judgement until QTc < 480 msec
	
--	--	---	--

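### Section 6.4 as shown has no pneumonitis rule, so a recovered, attributable Grade 3-4 pneumonitis defaults to restarting both drugs, and no text requires stopping

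*Combined protocol and SAP*

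**What the plan says.** **The default.** Under 5.4.1, an attributable non-hematologic toxicity of Grade 3 or higher is a dose-limiting toxicity (DLT). The exceptions are certain gastrointestinal events and dehydration, transient transaminase rises, and electrolyte disturbances that respond to oral replacement. No lung event is excepted. Section 6.1 has both drugs held after a DLT until Grade 1 or lower (or baseline, if that is higher), "and then palbociclib and ganitumab will be resumed with dose reduction according to Sections 6.2 (palbociclib) and 6.3 (ganitumab"). The exceptions to this default are toxicities given their own rule later in Section 6. There is a time limit: "If a patient cannot resume therapy within 21 days of holding palbociclib and ganitumab, they will be removed from protocol therapy". A patient who must permanently stop one agent "will be removed from protocol therapy altogether rather than continuing with monotherapy".

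**The specific rules.** Section 6.4 covers QTc prolongation (6.4.1), hyperglycemia (6.4.2) and infusion reactions (6.4.3). Section 6.5 covers hematologic toxicity.

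**Where pneumonitis appears.** A history of it excludes a patient (3.2.3). It is the stated reason for forbidding thoracic radiation on study (5.3.3). It is the one event listed as rare but serious for palbociclib (7.2). Section 7.3 reports five cases in a phase 3 trial of ganitumab with intensive chemotherapy, in patients who had earlier thoracic radiation.

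**Other exits.** Section 5.6 removes patients for "Intercurrent illness that prevents further administration of treatment" and for changes in condition that "render the participant unacceptable for further treatment in the judgment of the treating investigator". Its toxicity criterion refers back to Section 6. Section 5.4.1 adds: "Any dose-limiting toxicity should be reported immediately via email to the overall Principal Investigator and to the Study Coordinator".

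**The concern.** The two drugs have not been given together before, and the protocol links pneumonitis to each of them, although the evidence for ganitumab is narrower. It treats the event as serious enough that any past episode bars entry. Yet for a severe episode on study that is attributed to treatment and then clears, the written rule is to give both drugs again at a lower dose. Stopping is left to discretion.

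The stake is the safety of individual patients. No efficacy analysis or operating characteristic depends on this.

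**Working it through.** The plan states no figure to reproduce, and the documents give no pneumonitis rate for this combination, so no frequency is estimated. The check follows one case through the text: a first DLT, at starting doses, of attributable Grade 3 or 4 pneumonitis.

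1. **Is it a DLT?** Yes. It meets the Grade 3 or higher criterion in 5.4.1, and none of the exclusions applies.
2. **Does a specific rule displace the default?** None is visible. Sections 6.4.1 to 6.4.3 name other toxicities, and 6.5 is hematologic.
3. **What does the default do?** Section 6.1 holds both drugs and then restarts both at the next dose level in Tables 1 and 2:

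| Drug | Start | First reduction | Share of start |
|---|---|---|---|
| Palbociclib, Cohort A | 100 mg | 75 mg | 75/100 = 75% |
| Palbociclib, Cohort B | 125 mg | 100 mg | 100/125 = 80% |
| Ganitumab | 18 mg/kg | 12 mg/kg | 12/18 = 67% |

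4. **What recovery is needed?** Within a cycle, Grade 1 or lower (or baseline) suffices under 6.1. At the start of a new cycle, 5.2.2 is stricter. It requires "All other adverse events at baseline or" Grade 2 or lower, whichever is lower. Because a history of pneumonitis is excluded, baseline should be Grade 0, so full resolution is normally needed.
5. **What does the time limit do?** A patient who cannot restart within 21 days is removed. One who recovers in time is not.
6. **Do the corticosteroid limits matter?** Section 5.5.1.3 allows corticosteroids only for adrenal replacement, allergic reactions, prevention of transfusion reactions, inhaled or topical use, and stable or tapering doses in metastatic CNS disease. Pneumonitis is not listed. On its face, a patient on systemic steroids for pneumonitis could not restart, and one still on them at day 21 would be removed. A patient never given steroids, or weaned in time, is unaffected.
7. **Does anything else require stopping?** Section 5.6 removes the patient if the investigator judges further treatment unacceptable, but the trigger is that judgment. Its toxicity criterion returns to Section 6, which has no pneumonitis criterion. DLT reporting notifies the Overall Principal Investigator. The rule in 13.4 pauses cohort enrollment at 3 or more first-cycle DLTs among up to 12 patients and does not govern rechallenge of an individual.

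The path therefore ends in a restart of both drugs with no mandatory stop.

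**Completeness of 6.4.** Table numbers jump from 3 to 8, so four numbers (4 to 7) are unused. Only two unnumbered tables lie between, which leaves 4 - 2 = 2 unaccounted for. Section 5.4.1 also refers to 6.4 for raised liver enzymes, and 6.4 has no such text. Against a lost subsection, 6.4.1 to 6.4.3 run consecutively into 6.5 and Section 6 shows no redaction marks. Stale references are also plausible: 5.4.1 cites a Section 6.2.1 that does not exist in the current text.

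**The case against.** The strongest reply is that the existing safeguards leave few patients exposed, and that judgment suits a rare event. To be re-exposed, a patient must have a severe attributable event, recover within 21 days, be off any systemic steroids, and have an investigator who does not invoke 5.6. Cohort A patients have no effective standard option left (3.1.4.2). Some may have had lung radiation, which is allowed if at least 6 months have passed (3.1.6.2), so attribution may be uncertain and a fixed stop may remove someone who is benefiting. This stands as a limit on the size of the problem. It does not supply a rule that requires stopping. How often steroids would be used, and for how long, is an assumption that the documents do not settle.

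A reader might infer that pneumonitis is out of line because each toxicity named in 6.4 has some mandatory stop, such as "Remove from protocol therapy" for Grade 4 QTc prolongation. That comparison does not support a stop from Grade 3. Grade 3 QTc prolongation may restart, at the same dose if the cause is reversible. Grade 4 hyperglycemia without ketoacidosis or hyperosmolar syndrome may restart at 12 mg/kg. Non-hematologic DLTs not named in 6.4 follow the same default. The case for a stop rests on how the protocol itself treats pneumonitis at entry and during therapy.

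**Conclusion.** The point holds in a limited form, as a recommended change to a design choice. On the text shown, a first attributable Grade 3-4 pneumonitis that clears within 21 days leads by default to both drugs being restarted at 67% to 80% of their starting doses, and no provision requires stopping.

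A reader might go further and infer that the protocol forces rechallenge on every such patient, or leaves no way to stop. It does not: the 21-day limit, 5.2.2, 5.5.1.3 and 5.6 each narrow the group, and at most 33 patients are expected (13.2). Nor do the documents show pneumonitis as a ganitumab monotherapy effect. The five cases arose with intensive chemotherapy after thoracic radiation, and the monotherapy lists in 7.3 omit it.

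The conclusion assumes a first DLT with no earlier dose reductions, the reading of 5.2.2 given above, and that 6.4 is complete as shown. The last cannot be fully confirmed.

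**What to change.** First confirm against the full protocol that 6.4 contains no pneumonitis or hepatic text beyond what is shown. If it does not, add one pneumonitis/interstitial lung disease row to 6.4, stated as an exception to 6.1: for Grade 3-4 pneumonitis possibly, probably or definitely attributable to palbociclib or ganitumab, permanently discontinue both drugs and remove the patient from protocol therapy.

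This fits the existing structure. The last paragraph of 6.1 already ends protocol therapy when one agent must stop for good, and the toxicity criterion in 5.6 already points to Section 6. The DLT definition, monitoring rule, analysis and sample size do not change. The cost is one row in the next amendment, plus the loss of rechallenge for a rare benefiting patient, including one whose event may instead reflect earlier lung radiation.
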